5.0 Treatment Plan

Treatment will consist of nivolumab 480mg every 4 weeks and ipilimumab 1mg/kg every 8 weeks. Imaging assessments will be conducted every 8 weeks (+/- 2 weeks) for the first 24 weeks then every 8-12 weeks (+/- 2 weeks). If progression is noted on imaging in the setting of clinical stability, subjects may remain on study and have confirmatory imaging in 4-8 weeks per iRECIST criteria (see Appendix C)

Table 1: Treatment Plan

Version: 11/24/2020

CONFIDENTIAL

This material is the property of the University of Pennsylvania

Agent	Dose	Route	Frequency (within a 56-day cycle)
Nivolumab	480mg	IV infusion per institutional guidelines and the Package Insert	Days 1, 29
Ipilimumab	1mg/kg	IV infusion per institutional guidelines and the Package Insert	Day 1

5.1 Duration of Treatment

Subjects will continue on therapy until disease progression, unacceptable toxicity, withdrawal of consent, or two years of therapy. Subjects may remain on either ipilimumab or nivolumab monotherapy if the other agent is discontinued such as for toxicity.

6.0 Dosing Delays/Dose Modifications

The potential immune toxicities of nivolumab and ipilimumab are numerous, and no set of guidelines can account for all possible scenarios. Ultimately, subjects who experience toxicity related to nivolumab and/or ipilimumab will be managed according to standard clinical practice at the discretion of the treatment clinician, including the administration of corticosteroids. The toxicities for nivolumab and ipilimumab overlap considerably and it is uncommon that a toxicity be clearly attributed to only one of the agents.

Treatment algorithms for immune-related adverse events are provided in Appendix B for guidance. No dose modifications for nivolumab or ipilimumab are allowed. *Specific dose delays and the use of corticosteroids for toxicity is ultimately at the discretion of the treating physician.*

At the end of the study period, Bristol-Myers Squibb Company will not continue to supply study drug to subjects/investigators unless the Sponsor chooses to extend their study. The investigator is responsible to ensure that the subject receives appropriate standard of care or other appropriate treatment in the independent medical judgement of the investigator to treat the condition under study.

7.0 Study Procedures

Study procedures are further detailed in section 17.0 (Schedule of Events).

7.1 Tumor Analysis and Correlative Studies

7.1.1 Tumor Biopsy

Pre-treatment tissue biopsy is mandatory. Archival material cannot be substituted for the pre-treatment biopsy. Subjects in whom pre-treatment biopsy cannot be safely performed require approval of the Principal Investigator to enroll. On-treatment biopsies will be performed on cycle 1 between days 10-14 where safe and feasible, and we expect that this will be in the majority of patients. Testing of these samples may include studies of infiltrating T-

Version: 11/24/2020

CONFIDENTIAL

This material is the property of the University of Pennsylvania

cells such as subtyping, functional assays and receptor sequencing, whole exome or other genomic sequencing of the tumor, immunohistochemistry, and/or other assays that may be developed over the course of this study. Optional biopsies will be requested if a patient undergoes surgery that would permit tumor sampling such as laparoscopy and at disease progression. Procedures for tumor biopsy processing is described in detail in the laboratory manual.

7.1.2 Research Blood Sampling

Sixty mL total of blood in EDTA tubes for circulating tumor materials (circulating tumor cells, extracellular vesicles, and/or cell-free DNA) and peripheral blood mononuclear cells (PBMCs) will be collected at baseline prior to cycle 1 day 1 treatment on the same day as baseline biopsy (or within 3 days if not possible to perform same day), on cycle 1 between days 10-14 (same day as research biopsy if repeat biopsy performed), cycle 1 day 29, on day 1 of each subsequent cycle prior to treatment, and at the end of treatment visit.

A one-time 5mL sample in an EDTA tube will be drawn during screening, or, if not previously obtained, at a later treatment visit for storage of PBMCs for future germline sequencing with the [name] lab.

Procedures for research laboratory samples and processing is described in detail in the laboratory manual.

7.2 Assessment of Laboratory Measures and Disease Progression

7.2.1 Laboratory Safety Monitoring

CBC with differential will be assessed at screening, on days 1 and 29 of each treatment cycle, and at the end of treatment visit. Serum pregnancy will be assessed for women of childbearing potential at screening and every 4 weeks. Non-childbearing potential is defined in Appendix A. Serum chemistry labs will be assessed at screening, on days 1 and 29 of each treatment, and at the end of treatment visit. Serum TSH will be assessed at screening, on day 1 of cycle 2 and all subsequent cycles, and at the end of treatment visit.

For all laboratory measures, a window of +/- 3 days is acceptable.

7.2.2 Imaging Assessments

CT/MRI will be performed for disease assessment at screening (within 21 days of first doses of study drugs) and every 8 weeks (+/- 2 weeks). If progression is noted on imaging in the setting of clinical stability, subjects may remain on study and have confirmatory imaging in 4-8 weeks per iRECIST criteria. PET-CT is an acceptable substitute for CT/MRI if determined to be the standard of care by the treating physician.

7.3 Duration of Follow-Up

For this protocol, all subjects, including those who discontinue protocol therapy early, will be followed through review of the medical record for recurrence and survival for up to 3 years from their end of study visit (every 6 months for the first year, then annually for the second two years).

8.0 Study Treatment Details

8.1 Nivolumab

8.1.1 Other Names

Version: 11/24/2020

CONFIDENTIAL

This material is the property of the University of Pennsylvania

Opdivo

8.1.2 Classification

Nivolumab is a fully human immunoglobulin G4 (IgG4) monoclonal antibody that targets programmed cell death-1 (PD-1).

8.1.3 Mechanism of Action

Nivolumab selectively inhibits PD-1 activity by binding to the PD-1 receptor to block the ligands PD-L1 and PD-L2 from binding. The negative PD-1 receptor signaling that regulates T-cell activation and proliferation is therefore disrupted. This releases PD-1 pathway-mediated inhibition of the immune response, including the antitumor immune response.

8.1.4 Storage and Stability

The product does not contain a preservative. After preparation, store the nivolumab infusion either at room temperature for no more than 8 hours from the time of preparation (this includes room temperature storage of the infusion in the IV container and time for administration of the infusion) or under refrigeration at 2°C to 8°C (36°F to 46°F) for no more than 24 hours from the time of infusion preparation. Do not freeze.

8.1.5 Dose Specifics

480 mg IV over 30 minutes every 4 weeks

8.1.6 Preparation

Visually inspect drug product solution for particulate matter and discoloration prior to administration. Nivolumab [Opdivo] is a clear to opalescent, colorless to pale-yellow solution. Discard the vial if the solution is cloudy, discolored, or contains extraneous particulate matter other than a few translucent-to-white, proteinaceous particles. Do not shake the vial.

Withdraw the required volume of nivolumab [Opdivo] and transfer into an intravenous container. Dilute nivolumab [Opdivo] with either 0.9% Sodium Chloride Injection, USP or 5% Dextrose Injection, USP to prepare an infusion with a final concentration ranging from 1 mg/mL to 10 mg/mL. Mix diluted solution by gentle inversion. Do not shake. Discard partially used vials or empty vials of OPDIVO.

8.1.7 Administration

Administer the infusion over 30 minutes or per institutional guidelines through an intravenous line containing a sterile, non-pyrogenic, low protein binding in-line filter (pore size of 0.2 micrometer to 1.2 micrometer). Do not coadminister other drugs through the same intravenous line. Flush the intravenous line at end of infusion.

8.1.8 Availability

Nivolumab [Opdivo] is commercially available as a 40 mg/4 mL (10 mg/mL) and 100 mg/10 mL (10 mg/mL) solution in a single-dose vial. Only 100mg vials will be provided for this study.

8.1.9 Side Effects

Version: 11/24/2020

CONFIDENTIAL

This material is the property of the University of Pennsylvania

- Cardiovascular: Edema, peripheral edema, ventricular arrhythmia, pulmonary embolism, vasculitis
- Central nervous system: Fatigue, headache, peripheral neuropathy, peripheral sensory neuropathy, dizziness, peroneal nerve palsy, motor dysfunction, migraine, myasthenia, encephalitis, facial paralysis, Guillain-Barré syndrome, neuropathy
- Dermatologic: Skin rash, pruritis, vitiligo, exfoliative dermatitis, erythema, erythema multiforme, psoriasis, urticarial, palmar-plantar erythrodysesthesia
- Endocrine and metabolic: Hyponatremia, increased serum triglycerides, hyperkalemia, increased thyroid stimulating hormone level, hypocalcemia, increased serum cholesterol, hypercalcemia, hypothyroidism, hypomagnesemia, hypokalemia, hyperglycemia, hyperthyroidism, adrenocortical insufficiency, diabetes mellitus, diabetic ketoacidosis, weight loss, hypophysitis, pituitary insufficiency
- Gastrointestinal: Diarrhea, colitis, decreased appetite, increased serum lipase, nausea, constipation, vomiting, increased serum amylase, abdominal pain, duodenitis, gastritis, pancreatitis
- Hematologic: Lymphocytopenia, anemia, neutropenia, thrombocytopenia
- Hepatic: Increased serum AST, increased serum ALT, increased serum alkaline phosphatase, increased serum bilirubin, hepatitis, hepatic failure
- Immunologic: Antibody development
- Neuromuscular and skeletal: Weakness, musculoskeletal pain, back pain, arthralgia, spondyloarthropathy, limb pain, polymyalgia rheumatica
- Renal: Increased serum creatinine, renal disease, nephritis, renal insufficiency
- Respiratory: Upper respiratory tract infection, productive cough, cough, dyspnea, dyspnea on exertion, bronchopneumonia, pneumonia, pleural effusion, pneumonitis, respiratory failure, pneumonia due to *Pneumocystis jiroveci*
- Ophthalmic: Iridocyclitis, iritis
- Miscellaneous: Fever, infusion related reactions, hypersensitivity reaction, sarcoidosis

8.2 Ipilimumab

8.2.1 Other Names

Yervoy

8.2.2 Classification

Ipilimumab is a recombinant human IgG1 immunoglobulin monoclonal antibody that binds to the cytotoxic T-lymphocyte associated antigen 4 (CTLA-4)

8.2.3 Mechanism of Action

CTLA-4 is a down-regulator of T-cell activation pathways. Blocking CTLA-4 allows for enhanced T-cell activation and proliferation. In melanoma, ipilimumab may indirectly mediate T-cell immune responses against tumors. Combining ipilimumab (anti-CTLA-4) with nivolumab (anti-PD-1) results in enhanced T-cell function that is greater than that of either antibody alone, resulting in improved antitumor responses in metastatic melanoma.

8.2.4 Storage and Stability

The product does not contain a preservative. Store ipilimumab under refrigeration at 2°C to 8°C (36°F to 46°F). Do not freeze. Protect vials from light.

8.2.5 Dose Specifics

1mg/kg IV every 8 weeks

8.2.6 Preparation

Visually inspect drug product solution for particulate matter and discoloration prior to administration. Solution may have a pale yellow color. Discard the vial if the solution is cloudy, discolored, or contains extraneous particulate matter other than a few translucent-to-white, proteinaceous particles. Do not shake the vial.

Allow the vials to stand at room temperature for approximately 5 minutes prior to preparation of infusion. Withdraw the required volume of ipilimumab [Yervoy] and transfer into an intravenous bag. Dilute ipilimumab [Yervoy] with either 0.9% Sodium Chloride Injection, USP or 5% Dextrose Injection, USP to prepare an infusion with a final concentration ranging from 1 mg/mL to 2 mg/mL. Mix diluted solution by gentle inversion. Store the diluted solution for no more than 24 hours under refrigeration (2°C to 8°C, 36°F to 46°F) or at room temperature. Do not shake. Discard partially used vials or empty vials of ipilimumab [Yervoy].

8.2.7 Administration

Administer the infusion over 30 minutes or per institutional guidelines through an intravenous line containing a sterile, non-pyrogenic, low protein binding in-line filter. Do not coadminister other drugs through the same intravenous line. Flush the intravenous line at end of infusion.

8.2.8 Availability

Ipilimumab [Yervoy] is commercially available as a 50 mg/10 mL (5 mg/mL) and 200 mg/40 mL (5 mg/mL) solution in a single-dose vial. Only 200mg vials will be provided for this study

8.2.9 Side Effects

- Cardiovascular: Edema, peripheral edema, ventricular arrhythmia, pulmonary embolism, vasculitis
- Central nervous system: Fatigue, headache, peripheral neuropathy, peripheral sensory neuropathy, dizziness, peroneal nerve palsy, motor dysfunction, migraine, myasthenia, encephalitis, facial paralysis, Guillain-Barré syndrome, neuropathy
- Dermatologic: Skin rash, pruritis, vitiligo, exfoliative dermatitis, erythema, erythema multiforme, psoriasis, urticarial, palmar-plantar erythrodysesthesia
- Endocrine and metabolic: Hyponatremia, increased serum triglycerides, hyperkalemia, increased thyroid stimulating hormone level, hypocalcemia, increased serum cholesterol, hypercalcemia, hypothyroidism, hypomagnesemia, hypokalemia, hyperglycemia, hyperthyroidism, adrenocortical insufficiency, diabetes mellitus, diabetic ketoacidosis, weight loss, hypophysitis, pituitary insufficiency
- Gastrointestinal: Diarrhea, colitis, decreased appetite, increased serum lipase, nausea, constipation, vomiting, increased serum amylase, abdominal pain, duodenitis, gastritis, pancreatitis

- Hematologic: Lymphocytopenia, anemia, neutropenia, thrombocytopenia
- Hepatic: Increased serum AST, increased serum ALT, increased serum alkaline phosphatase, increased serum bilirubin, hepatitis, hepatic failure
- Immunologic: Antibody development
- Neuromuscular and skeletal: Weakness, musculoskeletal pain, back pain, arthralgia, spondyloarthropathy, limb pain, polymyalgia rheumatica
- Renal: Increased serum creatinine, renal disease, nephritis, renal insufficiency
- Respiratory: Upper respiratory tract infection, productive cough, cough, dyspnea, dyspnea on exertion, bronchopneumonia, pneumonia, pleural effusion, pneumonitis, respiratory failure, pneumonia due to *Pneumocystis jiroveci*
- Ophthalmic: Iridocyclitis, iritis
- Miscellaneous: Fever, infusion related reactions, hypersensitivity reaction, sarcoidosis

9.0 Statistical Plan

9.1 Endpoints

9.1.1 Primary Endpoint: Progression-Free Survival at 6 Months

Progression-free survival at 6 months (PFS6) is defined as the proportion of patients free from disease progression by iRECIST criteria (see Appendix D) or death at the time of week 24 restaging imaging (within acceptable 2 week window). Subjects who withdraw from the study prior to week 24 imaging will be considered to have progressed unless imaging is obtained at or after 24 weeks (within acceptable 2-week window), no progression is observed, and the subject has not initiated any other anti-cancer therapy prior to 6-month imaging. The final efficacy analysis will not be performed until all subjects have experienced progression or death, initiated additional anti-cancer therapy prior to 6 months from the start of study therapy (which will be considered progression), been lost to follow-up, or undergone at least six months of follow-up.

9.1.2 Secondary Endpoints

9.1.2.1 Progression-Free Survival

Progression-free survival is defined as the duration of time from start of treatment to time of progression, death, or last patient contact when progression-free. PFS will be calculated using both RECIST v. 1.1 (Appendix C) and iRECIST (Appendix D). For patients who are progression-free, PFS will be censored at the most recent date which documents progression-free status (i.e., scan date or clinical visit date).

9.1.2.2 Overall Survival

Overall survival (OS) is defined as the duration of time from start of treatment to death due to any cause or last patient contact alive. Public records (e.g. obituaries) may be used to ascertain dates of death for subjects where such data is not available in the medical record unless the subject withdraws consent for follow-up. For subjects who enroll in hospice care in whom the specific date of death cannot be determined, date of death will be recorded as the date the patient entered hospice. In subjects who are alive or lost to follow-up, OS will be censored at last date of contact alive.

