0.0 Study Summary

Title	Phase II Study of Nivolumab and Ipilimumab in Mucinous Colorectal and Appendiceal Tumors
Short Title	Nivo/Ipi In Mucinous CRC
IRB Number	831705
Protocol Number	UPCC 28218
Phase	Phase II
Methodology	Single Arm Phase II
Study Duration	18-24 months accrual plus 6 months follow-up
Study Center(s)	Abramson Cancer Center at University of Pennsylvania
Objectives	
Primary Objective
 
 1. To estimate six-month progression-free survival by iRECIST 
Secondary Objectives
 
 1. To determine overall response rate, duration of response, and progression-free survival by iRECIST and RECIST 1.1. To determine overall survival. 2. To estimate the toxicity rates by CTCAE v 5.0. 
Exploratory Objectives
 
 1. To measure T-cell subsets and markers of T-cell function in peripheral blood as a potential biomarker of response 2. To define the immune effects in pre- and post-treatment biopsy specimens with analysis of tumor-infiltrating lymphocytes, including immune subsets, mutational load, and TCR sequencing 3. To correlate imaging response with quantitative changes in cell-free tumor DNA, extracellular vesicles, and/or other circulating tumor materials

Number of Subjects	21
Diagnosis and Main Inclusion/Exclusion Criteria	
Inclusion Criteria:
 
 1. Colorectal or appendiceal mucinous tumor with peritoneal-only metastatic disease 2. Microsatellite stable by PCR and/or mismatch repair proficient by immunohistochemistry 3. ECOG PS 0-1 4. Standard laboratory parameters 5. Prior therapy with a fluoropyrimidine, oxaliplatin, and irinotecan unless contraindicated or refused. Prior treatment with antiangiogenic and/or anti-EGFR antibody therapy is permitted but not required 
Exclusion Criteria:
 
 1. Significant autoimmune disease 2. Bowel obstruction within the past 60 days 3. Use of systemic steroids other than for adrenal hormone replacement
Study Products, Dose, Route, Regimen	
Product: Nivolumab Dose: 480mg Route: IV Regimen: Every 4 weeks
 
Product: Ipilimumab Dose: 1mg/kg Route: IV Regimen: Every 8 weeks

Duration of administration	Subjects will continue on study therapy until disease progression, unacceptable toxicity, withdrawal of consent, or 24 months of therapy.

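### Overall survival can take in deaths found after last contact but censors everyone else at last contact, with no status date, so the Kaplan-Meier curve can be biased downward

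*Combined protocol and SAP*

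**What the plan says.** Section 9.1.2.2 gives the endpoint: "Overall survival (OS) is defined as the duration of time from start of treatment to death due to any cause or last patient contact alive". On finding deaths it says "Public records (e.g. obituaries) may be used to ascertain dates of death for subjects where such data is not available in the medical record", with one exception: "unless the subject withdraws consent for follow-up". On censoring it says "In subjects who are alive or lost to follow-up, OS will be censored at last date of contact alive".

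Section 7.3 says subjects "will be followed through review of the medical record for recurrence and survival for up to 3 years from their end of study visit", and gives the spacing as "every 6 months for the first year, then annually for the second two years". Section 9.2 estimates OS by Kaplan-Meier and gives the median with a 90% confidence interval.

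On timing, section 9.1.1 lets the final efficacy analysis proceed once every subject has had an event, been lost or had six months of follow-up, and section 0.0 gives the study duration as "18-24 months accrual plus 6 months follow-up". No section sets an OS cut-off date, a vital-status check of all subjects to a common date, or a rule for deaths that come to light only after last contact.

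**The concern.** Kaplan-Meier needs censoring that is unrelated to the outcome. Take two subjects last seen on the same day. One dies four months later and an obituary is found, so that subject stays in the analysis for those four months and counts as an event. The other is alive four months later with no new contact, and leaves the risk set on the day last seen. A public-record search of this kind can add deaths but never adds survival time.

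OS is a named secondary endpoint of a single-arm trial. It has no internal comparator, so an error in one direction is not cancelled by a control arm. Nor would a larger sample remove it.

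**Working it through.** **The plan's own figure.** The documents give no assumed OS, event count or loss rate. The only design figure is 81% power for 6-month PFS of 17% against 40% with 21 subjects. Rejecting at 7 or more of 21 gives P(X ≥ 7 | 0.17) = 0.053 and P(X ≥ 7 | 0.40) = 0.800. The normal approximation with two-sided alpha 0.10 gives 81.3%. The figure is reproduced, and OS censoring does not enter it.

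**Mechanism, by a constructed example (not an estimate of size).** Kaplan-Meier is S(t) = product of (1 − d/n) over death times. Suppose 10 subjects were all last seen at month 6 and the cut is at month 12. Three die at months 8, 9 and 10 and all three deaths are found; seven live.
- Current rule: the seven leave at month 6, so S = (1 − 1/3)(1 − 1/2)(1 − 1/1) = 0.
- Survivors followed to the cut: S = (1 − 1/10)(1 − 1/9)(1 − 1/8) = 7/10.

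**Simulation inputs.**
- From the documents: 21 subjects; 18 to 24 months of accrual; 6 months' minimum follow-up; visits about every 4 weeks on treatment; record review 6, 12, 24 and 36 months after treatment ends.
- Assumed: exponential OS with median 9 to 18 months; median time on treatment about 4 to 4.5 months; 0 or 20% lost after treatment ends; 0, 50% or 100% of lost subjects' later deaths found.

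**Bias of the current rule in 12-month OS, in percentage points, at a cut 6 months after accrual ends.** Columns two and three use 24-month accrual and let off-treatment contacts fall only on the review dates. Column four uses 21-month accrual, median OS 12 or 18 months, and a chart encounter every 1 to 2 months.

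| Lost; deaths found | Review dates only, median OS 9 | Review dates only, median OS 18 | Encounter every 1–2 months |
|---|---|---|---|
| none lost | −2.5 | −2.2 | −0.1 to −0.9 |
| 20%; all | −4.1 | −4.3 | −2.9 to −3.7 |
| 20%; half | −3.3 | −3.2 | about −2 |
| 20%; none | −2.3 | −2.0 | −0.4 to −1.0 |

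- With 18-month accrual, median OS 18, 20% lost, all deaths found and review-date contacts, the bias is −5.4. Across accrual lengths and medians, review-date contacts give about −3 to −6.
- Median OS, with review-date contacts, 20% lost and all deaths found: a true 18 months is typically estimated as 14.8, against 17.8 with complete follow-up. With frequent encounters and nobody lost, the median is off by about 0 to 0.7 months.
- If lost subjects have twice the hazard (20% lost, review-date contacts): −2.8 to −3.4 with all deaths found, −1.5 to −1.8 with half, about 0 with none.
- Later cuts: about 0 to −3 at 12 months after accrual; 0 to about −1 at 36 months.

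**Candidate repairs, same model, 20% lost.**
- Censoring everyone not found dead at the cut is unbiased if every death is found. It overstates 12-month OS by about 2 to 3 points if half of lost subjects' deaths are found, and by about 4 to 6 if none are.
- Following non-lost subjects to the cut, and censoring lost subjects at last contact without their later deaths, is within about 1 point of the truth when loss is unrelated to prognosis.

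**The case against.** The strongest objection is about size. Section 7.3 schedules when staff review the chart, not when patients are seen. A chart read at the data cut shows the latest clinical encounter, and the schedule of events in section 17.0 says post-study scans follow clinical care. If encounters are frequent, nearly all of the bias with nobody lost disappears. This stands, and it is why the lower end of the range is about half a point.

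Second, a reader might infer that deaths are counted at any time and that OS is certainly biased by several points. The documents do not support that. The public-record search is optional, applies only where the medical record lacks the date, and excludes subjects who withdraw consent for follow-up. What the text lacks is a cut-off. If lost subjects have worse survival and few of their deaths are found, the downward bias can vanish.

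Third, it is tempting to conclude that everyone not found dead should simply be censored at a common date. That is safe only if the search finds every death. Section 9.1.2.2 offers obituaries as an example and describes no complete source, so this rule could err upward by as much as the present one errs downward.

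Fourth, OS is secondary, has no hypothesis or threshold, and section 9.2 gives no OS benchmark. With 21 subjects a 90% interval around 50% is about ±1.645 × √(0.25/21) = ±18 points, wider than any bias shown here. That limits the consequence. It does not justify leaving in a one-directional error that is cheap to reduce.

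**Conclusion.** The concern holds as a gap in the OS rule. Section 9.1.2.2 as written lets follow-up depend on outcome, and Kaplan-Meier OS can be biased downward. Twelve-month OS is low by about 0.5 to 6 points at a cut 6 months after accrual ends, and by about 0 to 3 points at a cut 12 months after. Little remains after long follow-up. These figures rest on assumed survival, time on treatment, loss, death capture and contact frequency, none of which the documents give. The upper end needs sparse chart contacts, appreciable loss and near-complete capture of lost subjects' deaths. A reader should not infer that the trial's main conclusion is at risk: 6-month PFS and its 81% power do not depend on this rule.

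**What to change.** Amend section 9.1.2.2 along these lines:

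- Before each OS analysis, set one status date, early enough before the search for routine chart entries to fall after it.
- Check every subject who has not withdrawn consent for follow-up, in the medical record and the same public sources, as of that date.
- Count deaths only up to the status date.
- Censor subjects whom the check confirms alive at the status date.
- For subjects truly lost, censor at last contact and do not count deaths found only afterwards in public records. Define lost from contact history alone, without regard to whether a death was found; otherwise the asymmetry returns.
- Report two sensitivity analyses: (a) all deaths found are counted and those not found dead are censored at the status date, which overstates OS if capture is incomplete; (b) the current rule, which tends to understate it.

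The cost is SAP wording and one record search per analysis for the 21 evaluable subjects, plus any replaced under section 4.3.1. A few late deaths among lost subjects drop out of the primary OS estimate. If lost subjects do worse than the rest, that estimate will be somewhat high, so the two sensitivity analyses should be shown beside it.
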